### Measures Table

Variable	Item #	Content & references	R
Primary outcomes			
Infant develop. knowledge	30	Higher score indicates higher knowledge of infant development 	FR
Father role beliefs	15	Higher score indicates more positive beliefs in father's role in child care 	FR
Attachment beliefs	35	Higher scores indicate more positive beliefs about fetal/infant attachment 	FR
Parenting self-efficacy	17	Higher score indicates greater confidence in overall parenting skills 	FR/MR
Infant care self-efficacy	15	Higher score indicates greater confidence in infant care 	FR/MR
Cooperative coparenting	10	Higher scores indicate greater coparenting agreement & support 	FR/MR
Secondary outcomes			
Partner relationship quality	12	Higher score indicates greater perceived partner relationship quality (T2) 	FR/MR
Infant care behaviors			
Infant engagement	17	Higher score indicates higher father engagement in infant care activities 	FR/MR
Time spent with infant	2	Days per week spent with infant; Hours per day spent with infant 	FR/MR
Safe sleep care	14	Higher score indicates greater adherence to 6 safe sleep AAP guidance 	FR
Injury prevention care	12	Higher score indicates greater adherence to 5 child injury AAP risk areas 	FR
Moderator factors			
Resident status	3	Living together with mother (current; history of gap; length of gap)	FR/MR
Caregiver conflict	12	Higher score indicates greater perceived caregiver conflict 	FR/MR
Partner relationship quality	12	Higher score indicates greater perceived partner relationship quality (T1) 	FR/MR
Background factors			
About parents	8	Age, race/ethnicity, income, education, occupation, # people in household, relationship status, prior parenting experience, exposure to pregnancy/parenting/infant care info  , father present at prenatal, birth, WCC	FR/MR
About father	22	Personal health behaviors (substance use, irritability)	FR/MR
About infant	6	Sex, gestation weeks, birth weight; WCC receipt	FR/MR
Process measures			
Technology usability	12	Higher score indicates greater technology usability 	FR
Technology acceptance	8	Higher score indicates greater technology acceptance 	FR
Intervention satisfaction	1	Higher score indicates greater intervention satisfaction 	FR

R=Reporter; FR=Father report; MR=Mother report; WCC=Well-child care; T1=Time 1; T2=Time 2; AAP=Am Academy of Pediatrics

b. Study duration and number of study visits required of research participants.

The study will last 7 months. Participants will be recruited through 25 weeks of gestation and followed 2 months after the infant's birth. For fathers who meet the study criteria and consent to participate in the study, they will complete two study visits: a survey at baseline and another at 7-month follow up; fathers assigned to the Text4Father in the interim will receive approximately two texts a week for 7 months. For mothers who meet the study criteria and consent to participate in the study, they will complete two study visits: a shorter survey at baseline and another at 7-month follow up. All study participants (fathers and mothers) will receive text at the beginning a flyer jpeg about the study to share with their partner and 3 interim texts (1 text each at 2 months, 4 months, and 6 months) that will assess distress and perceptions of caregiver conflict between the father and other caregivers.

c. Blinding, including justification for blinding or not blinding the trial, if applicable.

This will not be a blinded study. The intervention consists of receiving text messages which, by definition, is a non-blinded activity.

d. Justification of why participants will not receive routine care or will have current therapy

stopped.  
Not applicable.

e. Justification for inclusion of a placebo or non-treatment group.  
Not applicable.

f. Definition of treatment failure or participant removal criteria.  
For the purposes of this behavioral study, treatment failure is not applicable. Criteria for participant removal: if system error from text messaging platform indicates that a participant's cell phone number is no longer active and we are unable to contact participants' shared contacts after no more than 3 attempts with each contact in the first 10 days that is repeated no more than twice thereafter.

g. Description of what happens to participants receiving therapy when study ends or if a participant's participation in the study ends prematurely.  
Participation in this study will not impact participants' usual care regardless of how the study ends or if a participant's participation in the study ends prematurely.

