**Figure 1. Overview of Study Procedures**

**Table 1. Schedule of Activities**

	pre-screening Pre- consent)	(Visit 1/ Time 1)	(Visit 2/ 2 months)	(Visit 2/ 4 months)	(Visit 3/ 6 months)	(Visit 2/ Time 2/ 7 months+/ weeks)
Review eligibility (phone/in-person)	X					
Informed consent (phone/in-person)		X				
Demographics/background characteristics		X				
Outcome evaluation						
Parent knowledge, self-efficacy, behavior survey		X				X
Intervention acceptability survey						X
Monitoring responsive texts			X	X	X	
Randomization		X				
Control & Experimental Interventions – Text4Father		X	X	X	X	
Adverse Events Reporting		X	X	X	X	X

**Setting.** We will conduct this study and recruit participants in Baltimore. Baltimore is a community with marked health disparities related to maternal and infant outcomes. In 2015 in Baltimore, the infant mortality rate was almost 2 times higher for black (9.7/1,000 live births) than white infants (5.4/1,000); this rate was 1.3 times greater than Maryland's rate, and 12% of babies born were low birthweight versus a national average of 8%. Settings will include the Hopkins Maternal-Fetal Medicine (MFM) Clinic and Fetal Assessment Center where we successfully collaborated for the 6-week feasibility pilot that informs this proposal. [name], Professor and Director of the Johns Hopkins' Division of MFM, facilitated MFM staff education for the pilot and is committed to ensuring this project's feasibility. The Center sees over 21,000 fetal ultrasound exams and delivers over 2,400 babies each year. The majority of patients are publicly insured (62%) and half are African American. Based on our preliminary work, we estimate that 865 infants each year will have first-time lower income fathers.

**Participants and Recruitment.** Research staff will recruit 120 adult expectant fathers and their female partners (120 pregnant females) (60 dyads per study arm) from the Hopkins' MFM Clinic and Fetal Assessment Center to be enrolled through 25 weeks gestation. The index participant and their partner will contact study staff to be scheduled for a research visit. An eligibility screener will be individually completed with both members of the dyad to determine study eligibility. Our target is to have complete data on 48 dyads so we set sample size at 60 in order to account for attrition.

[figure not shown]

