**Figure 2. Text4Father Study Recruitment Algorithm**

### Intervention.

**Conceptual Framework.** This study is informed by the Integrated Behavioral Model (IBM) that asserts behavior (i.e., father engagement) is influenced by core constructs of behavioral attitudes, perceived norms, and personal agency (Figure 1). Each construct is determined by underlying beliefs: attitudes are specific beliefs about performing a behavior, perceived norms are influenced by what others think about behavioral performance, and personal agency is one's confidence to perform the behavior (self-efficacy). Other constructs (e.g., background factors) influence behavior via these beliefs. Text4Father content focuses on improving fathers' knowledge of infant development, father role beliefs, attachment beliefs, parenting self-efficacy, infant care self-efficacy, and cooperative coparenting (primary outcomes)

that may result in increased partner relationship quality and behavioral engagement in infant care (i.e., specific activities and time spent with infant, use of infant safe sleep and

**Fig 1. Conceptual Framework  
of Text4Father Intervention**

injury prevention behaviors) at follow-up. We are also interested to explore whether fathers' baseline resident status, partner relationship quality, and caregiver conflict moderate the association between intervention receipt and study outcomes.

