### **Quality Control**

**1. Quality Control-Treatment Fidelity.** Drs. [name], [name], and [name] will train and supervise research staff to ensure appropriate protocol execution. Research staff will activate Text4Father for consented participants randomly assigned to the intervention. [name] will continually monitor and document fidelity via: 1) Technical functionality (Does technology operate as intended?) assessed by confirming that the system sends the welcome text and is received by participants at enrollment; 2) Technical stability (Does technology consistently operate as intended?) assessed by ensuring texts are consistently delivered as intended with minimum system failures/bounce backs. At the follow-up visit, study staff will ask participants assigned to the intervention arm to verify text receipt as well as to record unread texts. Study staff will ask them to open their phone to view the number of unread texts and then record the number of unread texts from Text4Father. If no texts are present, they will be asked why the texts were deleted. Study staff will also record texts that were received to ensure technical stability. The study team will also ensure 3) Technical quality assessed by keeping content up-to-date.

**2. Recruitment Screener.** Includes collection of basic demographic data and the outcome of recruitment effort so that we can keep an accurate account of referral patients who are ineligible and/or refuse to participate in the intervention.

**3. Surveys.** We developed a survey to collect information about fathers' knowledge, self-efficacy, and behavioral engagement in parenting and infant care, as well as technology acceptability.

From fathers, we will collect self-report responses about their background sociodemographic factors, including use of other pregnancy/parenting/infant care resources, perceptions of caregiver conflict, and about their infant, as well as their knowledge, self-efficacy, beliefs, and behaviors related to involvement in pregnancy and with their infant, cooperative coparenting, and relationship quality with partner and personal health behaviors, using a survey instrument at baseline and at 2 months of postnatal age (7-month follow-up) in-person, via phone, or electronically via Qualtrics. At follow-up (7-months), we will also assess intervention fathers on technology usability, acceptability, and satisfaction. This survey takes about 40-45 minutes to complete.

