### Statistical methods

**Aims 1 and 2. Feasibility and Acceptability.** Using completed clinic appointment, screener, and consent data, we will assess feasibility of overall recruitment by calculating the proportion of eligible fathers who consent to study participation and recruitment by resident status. Based on our pilot work, we anticipate recruiting  $\geq 70\%$  of fathers who are approached. We will calculate feasibility of retention as the proportion of enrolled participants who complete 7-month follow-up survey (2-months of postnatal age). We will calculate study retention overall and separately by treatment assignment and use Chi-square tests to determine if we achieved follow-up of  $\geq 80\%$  by treatment assignment.

In the Text4Father arm, we will calculate the proportion of individuals completing the

intervention and assess at exit these participants' technology usability (12 items), acceptance (8 items), and satisfaction (1 item) (on 5-point scales from "strongly disagree" to "strongly agree"). We will examine whether we achieved  $\geq 75\%$  agree/strongly agree usability/acceptability rates and generate means (SD) for each.

**Aim 3. Efficacy.** We will examine the effect of the randomization scheme and explore missing data due to survey non-response and attrition. We will then apply separate random intercept coefficient regression models for each study outcome accounting for two levels of nesting (repeated measures and individuals). Each model will estimate differences among intervention and usual care control arms identifying change in each study outcome between baseline and follow-up. This type of analysis will allow for examining 1) within-individual change over time in an outcome, accounting for dependency among observations within individuals by modeling within-person error, 2) between-individual variation over time, and 3) between-subjects effects based on group assignment to identify significant differences in content (Text4Father) as compared to usual care. Our sample size should be large enough to adequately power analyses for examining change in fathers' engagement (see below). The fixed effects from these analyses will help determine the expected effect size for other outcomes to inform power calculations for a larger R01-funded trial.

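### Attachment beliefs, one of six primary outcomes, appears to refer to a fetus at baseline and an infant at follow-up; the plan should adjust for the baseline score rather than model raw change

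*Combined protocol and SAP*

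**What the plan says.** The Measures Table (section 4) lists attachment beliefs among six primary outcomes. It is a single father-reported row of 35 items, described as "Higher scores indicate more positive beliefs about fetal/infant attachment". It is the only row in the table that names two objects. It carries no wave label and no division of items by wave.

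On timing, section 4, item b says: "Participants will be recruited through 25 weeks of gestation and followed 2 months after the infant's birth". The Surveys paragraph of section 4 gives fathers the survey at those two points only. The first therefore falls before birth and the second after it.

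Section 7, Statistical methods, Aim 3 applies a separate random-intercept model to every outcome, "identifying change in each study outcome between baseline and follow-up". It lists "within-individual change over time in an outcome" as the first thing the analysis will examine. It describes no baseline-adjusted analysis, no scoring by wave and no linking of scores.

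**The concern.** A change score means something only if the same quantity is measured twice. If fathers answer about a fetus at baseline and an infant at follow-up, the difference between the two scores mixes a change of content with any change in the father. The time effect and the within-arm change for this outcome could then not be interpreted.

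The arm comparison faces a different and smaller problem. Raw change subtracts the baseline one for one, whatever its relation to the follow-up score. If the two are only weakly related, the subtraction adds noise. This matters because the trial's stated purpose is to supply effect sizes, and its fixed effects are to inform the power of a larger trial.

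**Working it through.** **Inputs from the documents.** 60 fathers per arm, 20% attrition, a target of 48 complete dyads per arm, d = 0.472 and 80% power (sections 4 and 7). Randomisation follows the baseline survey (section 4, Randomization Schedule).

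**Assumptions.** The documents do not give alpha, sidedness, the cross-wave correlation (rho) or the ratio k of baseline SD to follow-up SD. I take two-sided alpha 0.05, set the follow-up SD to 1, and vary rho and k.

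**The plan's own figures.** Attrition reproduces: 48 / (1 − 0.20) = 60. The 80% power does not follow from the stated inputs alone. Comparing follow-up scores and ignoring baseline gives 63% at 48 per arm and 73% at 60 per arm. At 48 per arm and equal SDs, 80% needs rho of about 0.57 with baseline adjustment or about 0.66 with raw change. The stated power may rest on an unreported correlation, so it cannot be called wrong.

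**Variance of the arm contrast, n per arm**
- Raw change: (2/n)(k² + 1 − 2·rho·k). With two complete waves, the arm-by-time term of a random-intercept model is this difference in mean change.
- Follow-up adjusted for baseline: (2/n)(1 − rho²).
- Difference between the brackets: k² + 1 − 2·rho·k − (1 − rho²) = (k − rho)². This is never negative, so adjustment is never less precise, apart from one degree of freedom.

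**Example, k = 1, rho = 0.2, n = 48**
- Change: SE = √(2 × 1.60 / 48) = 0.258; 0.472 / 0.258 = 1.83; power 44%.
- Adjusted: SE = √(2 × 0.96 / 48) = 0.200; 0.472 / 0.200 = 2.36; power 65%.

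**Results** (noncentral t, 94 and 93 degrees of freedom)

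| k | rho | Variance bracket, change | Variance bracket, adjusted | Power, change | Power, adjusted |
|---|---|---|---|---|---|
| 1.0 | 0.2 | 1.60 | 0.96 | 44% | 65% |
| 1.0 | 0.3 | 1.40 | 0.91 | 49% | 67% |
| 1.0 | 0.5 | 1.00 | 0.75 | 63% | 75% |
| 1.0 | 0.66 | 0.68 | 0.56 | 79% | 86% |
| 0.7 | 0.5 | 0.79 | 0.75 | 73% | 75% |
| 1.3 | 0.5 | 1.39 | 0.75 | 49% | 75% |

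With equal SDs and rho below 0.5, raw change has less power than ignoring the baseline (63%). At k = 0.7 and rho 0.66 the two methods are practically level, since (0.7 − 0.66)² = 0.0016.

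**Effect of a content shift.** I simulated 8,000 trials with 48 per arm, rho 0.3, k = 0.8 and a 1 SD shift between waves common to both arms. Control fathers showed a mean within-father change of 1.00 although none had truly changed. The arm estimate was 0.472 for a true 0.472, and type I error with no effect was 5.2%.

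**The case against.** The strongest reply is that the change of object is inferred. No section describes two forms, a division of items or items that do not apply at one wave. Parallel items reworded for fetus and infant, or general belief items that can be answered at both times, fit the table's wording equally well. This stands. A reader might infer that the instrument definitely switches and that within-father change is an artefact; the documents support only that the content appears to differ and that nothing links the two scores.

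Second, the aim is a comparison with usual care, and that comparison is not harmed in validity. This also stands. A reader might infer a biased treatment effect, but baseline precedes randomisation and both arms are described as taking the same outcome survey, so a content shift cancels between arms.

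Third, baseline adjustment is at least as precise as raw change for any outcome measured twice, so the precision argument is not peculiar to attachment. That is true. What is particular here is the reason to expect a weak correlation or unequal SDs. How large the loss is remains unknown: from almost nothing to more than 25 percentage points of power over plausible inputs.

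Finally, this is one of six outcomes labelled primary in a preliminary-efficacy study, and the outcome boxes that open section 7 enter only the Parenting Sense of Competence as primary. That limits the consequence. It does not argue against a correction that costs almost nothing.

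**Conclusion.** The point holds in a conditional form. The plan models raw change on an outcome whose content appears to differ between surveys, and does not say how the two scores relate. Unless the items are common or linked, mean within-father change in attachment beliefs should not be interpreted.

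The arm contrast is unbiased, so the remaining issue is precision. At 48 completers per arm, two-sided alpha 0.05, d = 0.472 and equal SDs, moving from raw change to baseline adjustment raises power by about 21 percentage points at rho 0.2, 12 at rho 0.5 and 7 at rho 0.66. At rho 0.5 the gain is 2 points if the baseline SD is 0.7 times the follow-up SD, and 26 points if it is 1.3 times. The correlations and SD ratios are assumptions. The results do not show that the stated 80% power is wrong, because a correlation of about 0.66 with equal SDs would deliver it under raw change.

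**What to change.** In section 7, Aim 3, define the arm effect on attachment beliefs as the follow-up score regressed on arm with the baseline score as a covariate, in place of the arm difference in raw change. The two scores need not share a metric for this: linear rescaling of the covariate, including standardising it, leaves the adjusted arm effect unchanged.

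In the Measures Table, state which items are asked at each wave and how each wave is scored. If the items differ, label the T1 and T2 scores separately and neither report nor interpret within-father change for this outcome. If they are common or linked, say so; within-father change can then stay.

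The cost is wording in two places. The baseline score is already collected, so no new data are needed. Within-father change is lost for this one outcome, and only if the forms differ.

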Text4Father is a multi-modal texting program consisting of approximately twice-weekly texts written at a 5th grade reading level to initiate between 20-25 weeks gestation. Texts include resource links and instructions to support behavior change (e.g., videos, infographics) and start mid-pregnancy and continuing through 2 months of age. Text content provides a father with educational/informational guidance to support his infant, partner, and own well-being. Content was developed with feedback from the target population, consensus-building with experts, and an evidence-based review (see Prelim Studies). Text4Father is programmed to push/receive texts that tailor content receipt based on: gestational age/infant age after birth and father's resident status, and will remind fathers to share updates. When developing texts, we relied on evidence about writing text messages for behavior change: 1) using motivational language rather than just information; 2) actively involving learners with specific tasks to complete related to the desired behavior change; 3) sharing credible information; and 4) personalizing and tailoring messages. Personal health information will not be shared or requested as part of the text messaging platform.

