We will use SMS services through a licensed commercial provider such as EngageSpark, TextNow, or RapidSMS for communicating with father and mother participants in all arms of the study. Each of these companies allow for texting and calling and can be enabled for use on a phone, tablet, or computer that makes this platform optimal for this study. Further, each of these companies has strict policies to protect the user to prevent unauthorized disclosure of information and physical, electronic, and procedural safeguards are in place according to industry standard procedures and security procedures. Research staff will be responsible for monitoring fidelity of the texts sent and using the online account to register and send any interim text-message to participants in the study. Since a telephone number is created with each account, the telephone number will be recognizable to participants as Text4Father communication.

Finally, all participants will be encouraged to use standard safety mechanisms such as a pin or password to lock access to their cell phones by others, if not already in place.

**Control Groups.** The usual care arm will receive 3 interim texts (1 text each at 2 months, 4 months, and 6 months) that will assess distress and perceptions of caregiver conflict between the father and other caregivers. The usual care arm will not receive any additional interaction since maternity care typically does not provide any organized educational approach.

For ethical reasons all arms will receive at baseline a new parent handout about local birth resources/hotlines.

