### **End-of-Study Definition**

A participant is considered to have completed the study if he has completed the baseline assessment, participation in Text4Father if assigned to this study arm, and the 7-month follow-up assessment. The end of the study is defined as completion of the 7-month follow-up assessment as shown in the Table 1 Schedule of Activities.

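### The participant-removal rule starts from a text-platform error that can arise far more often in Text4Father fathers than in usual-care fathers, so detection, and possibly removal, can differ by arm

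*Combined protocol and SAP*

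**What the plan says.** Section 4, item f, gives one removal criterion with two parts, joined in a single condition: the participant's "cell phone number is no longer active and we are unable to contact" the people listed as contacts. The first part is the trigger: "if system error from text messaging platform indicates that a participant's cell phone number is no longer active". The second is that staff are "unable to contact participants' shared contacts after no more than 3 attempts with each contact in the first 10 days", a round that may be repeated at most twice. No other trigger is given. The limits on attempts are maxima, and no minimum is set.

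The number of texts depends on arm. Under item b, "fathers assigned to the Text4Father in the interim will receive approximately two texts a week for 7 months"; the Intervention section starts the programme between 20 and 25 weeks of gestation. For controls, the Control Groups paragraph says "The usual care arm will receive 3 interim texts", at months 2, 4 and 6. Item b also gives all fathers and mothers those three texts, plus a flyer text at the start. Section 8, item b, however, limits the two-monthly text queries to all mothers and intervention fathers. The bullets for father participants that follow do not name an arm.

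Section 7 (Aims 1 and 2) defines retention as completion of the 7-month survey among those enrolled, with a target of at least 80%, examined by arm. The End-of-Study Definition is different: completion also requires "participation in Text4Father if assigned to this study arm". The documents do not say whether a removed father is still approached at 7 months or kept in the analysis.

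**The concern.** Whether a father enters the removal process depends on a text being sent while his number is inactive. In the Text4Father arm a text goes out every few days, and Quality Control has staff watching for bounce-backs. In usual care there are three occasions, or none, and no equivalent check is described. The same temporary lapse can therefore start the process in one arm and go unseen in the other.

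Two results are exposed. By-arm retention is a feasibility endpoint, and a procedure that operates more often in one arm can move it. The efficacy contrast can also be affected if the fathers removed differ in how their outcomes change. Both results are meant to inform a larger trial. Mothers are not affected in this way, because their texts are the same in both arms.

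**Working it through.** **1. The plan's own figure.** 48 complete dyads with 20% attrition: 48 / (1 − 0.20) = 60 per arm. This reproduces. One father is 1/60 = 1.7 percentage points of retention.

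**2. Sends at which the error can arise.**
- Text4Father, two a week for 7 months (30.4 weeks): 2 × 30.4 = 61.
- Text4Father from the gestational start, assuming birth at 40 weeks and 8.7 weeks to 2 months of age: 2 × (20 + 8.7) = 57 from week 20, and 2 × (15 + 8.7) = 47 from week 25.
- Usual care: 3 interim texts, or 0 under section 8.
- The flyer adds one text for everyone. It goes out at the start, so it cannot detect a mid-study lapse.

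**3. Share in whom the error is raised.** The documents give no lapse rate. Assume 20% of numbers go inactive by month 7 at a constant hazard, so P(inactive by month t) = 1 − 0.8^(t/7).
- Text4Father: 60 evenly spaced sends are about 3.5 days apart, with the last at 60 × 7/61 = 6.89 months. Any spell of a week or more before then meets a send: 1 − 0.8^(6.89/7) = 19.7%.
- Usual care, permanent loss: the error is raised if the loss precedes month 6: 1 − 0.8^(6/7) = 17.4%. The mean delay to detection is about 31 days, against 2 in Text4Father.
- Usual care, lapse of length L: the error is raised only if the lapse begins within L before month 2, 4 or 6. Simulation with 2 million draws gives 8.6% for 1 month and 4.3% for 2 weeks.

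**4. Removal gap.** Gap = (Text4Father share − usual-care share) × P(contacts fail). The last term is not in the documents; assume 0.5.

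| Case | Text4Father | Usual care | Detection gap, fathers of 60 | Removal gap, points |
|---|---|---|---|---|
| Permanent loss | 19.7% | 17.4% | 1.4 | 1.2 |
| 1-month lapse | 19.7% | 8.6% | 6.7 | 5.6 |
| 2-week lapse | 19.7% | 4.3% | 9.3 | 7.7 |
| No usual-care texts | 19.7% | 0% | 11.8 | 9.9 |

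**5. Range.** With 10% to 30% of numbers going inactive, the detection gap is 0.7 to 2.0 fathers of 60 for permanent loss and 3.4 to 10.1 for 1-month lapses. At 50% contact failure these are removal gaps of 0.6 to 1.6 and 2.8 to 8.4 points. Every gap scales with the contact-failure rate: at 25% failure the column in step 4 halves, to 0.6, 2.8, 3.9 and 4.9 points.

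**The case against.** A platform error alone removes nobody. The contact step must also fail, and it is the same in both arms. Safeguards apply to both arms as well: section 10 pays participants who report contact changes, follow-up may be in person, by phone or online, and the partner is enrolled and linked by identifier. For a permanently dead number, three texts find nearly as many fathers as sixty (17.4% against 19.7%). Retention is counted among all enrolled, so removal does not change the denominator, and a father with a dead number and unreachable contacts may be lost in either arm. All of this stands, and it limits the size.

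A reader might go further and infer that removal is built to differ by arm and inflates the treatment effect. The documents do not support that. Under the three-text version the gap may be about one point. Earlier detection also starts earlier tracing, which could improve Text4Father retention. A consistently lower score among removed fathers does not by itself give a bias of matching size, because Aim 3 models change from baseline to follow-up; bias would need a difference in change, for which the documents give no figure.

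What the objection does not remove is that the trigger is checked far more often in one arm, no arm-neutral check is described, and the handling of removed fathers is left open.

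**Conclusion.** The point holds as a risk, not as a demonstrated bias. Entry into the removal process depends on arm, so detection, and possibly removal, can differ. Assuming 20% of numbers go inactive and contacts fail half the time, the removal gap is about 1 point for permanent loss, about 6 to 8 points for temporary lapses, and about 10 points if usual-care fathers get no texts.

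As effects on retention these are upper limits for those assumed rates. Some removed fathers would be lost anyway, and a short lapse may end before the contact attempts do. Half may also be too high a contact-failure rate if the partner counts as a listed contact, which the rule does not say. By-arm retention can be distorted and the efficacy contrast can be biased, but neither the direction nor the size of that bias is established. The change is worth making because it is cheap.

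**What to change.** - In section 4, item f, state that an inactive number ends message sending, not study participation.
- Attempt the 7-month survey for every randomised father in both arms on the same contact schedule, including through the enrolled partner.
- In section 7, state that fathers are analysed as randomised, including those whose numbers became inactive.
- Reconcile Control Groups, section 4 item b, section 8 item b and the father-participant bullets on whether usual-care fathers receive the interim texts.
- Optionally, align the End-of-Study Definition with the survey-based retention definition in section 7. The retention calculation does not depend on this, but the two definitions now treat the arms differently.

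The cost is protocol wording and a few more contact attempts at follow-up.
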